6.1 DETERMINATION OF SAMPLE SIZE

This is an exploratory study for which no formal statistical hypothesis will be tested, and therefore the sample size is chosen to estimate the absolute bioavailability of the 10 mg single dose with sufficient precision.

A total of 8 subjects per cohort are to be enrolled with the target of at least 6 subjects available for the primary PK analysis (i.e., having taken a single dose of 10 mg on Day 1 and completed all PK assessment up to Day 10). If the number of subjects providing PK data from the multiple dose parts of the study is lower than 6 for either cohort more subjects may be enrolled.

Assuming a within-subject variability of around 35% it can be estimated that with 6 subjects the half-width of the 90% confidence interval (CI) for the ratio of geometric means of the microdose IV kinetics with that from the oral dose (i.e. CL versus CL/F) would be obtained by dividing/multiplying the ratio estimate by a factor of 1.50.

The within-subject variability value of around 35% has been identified as a reasonable assumption: it is smaller than the observed 42% between-subject variability for the apparent clearance of distribution (CL/F) from a single oral 10 mg dose in study WP40038, and it considers that the reference will be obtained from IV kinetics, which is expected to be less variable than oral kinetics.

Table 4 Precision Factor Estimates

Number of Subjects	Variability	Precision Factor
6	30%	1.42
	35%	1.50
	40%	1.59

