## 6.1 Sample Size Considerations

This is an exploratory study for which no formal statistical hypothesis will be tested, and therefore the sample size is chosen to estimate the absolute bioavailability of the 10 mg single dose with sufficient precision. A total of 8 subjects per cohort are to be enrolled with the target of at least 6 subjects available for the primary PK analysis (i.e., having taken a single dose of 10 mg on Day 1 and completed all PK assessment up to Day 10). If the number of subjects providing PK data from the multiple dose parts of the study is lower than 6 for either cohort more subjects may be enrolled.

Assuming a within-subject variability of around 35% it can be estimated that with 6 subjects the half-width of the 90% confidence interval (CI) for the ratio of geometric means of the microdose IV kinetics with that from the oral dose (i.e. CL versus CL/F) would be obtained by dividing/multiplying the ratio estimate by a factor of 1.50. The within-subject variability value of around 35% has been identified as a reasonable assumption: it is smaller than the observed 42% between-subject variability for the apparent clearance of distribution (CL/F) from a single oral 10 mg dose in study WP40038, and it considers that the reference will be obtained from IV kinetics, which is expected to be less variable than oral kinetics.

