### 9.4.3 Hypothesis Testing

No formal hypothesis testing will be done.

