### 16.2.2 Pharmacokinetic Parameters

Plasma PK parameters for balovaptan, [C]-balovaptan, M2 and M3, will be estimated using non-compartmental methods with WinNonlin®.

The plasma PK parameters will be estimated from the concentration-time profiles. In estimating the PK parameters, BQL values will be set to zero for the pre-dose PK sample, as well as for all other samples being BLQ and occurring before  $t_{max}$ . For subsequent time points, the result will be set to missing. Actual sampling times, rather than scheduled sampling times, will be used in all computations involving sampling times. If the actual time or dose time is missing, the scheduled time may be substituted in order to calculate the PK parameter.

Descriptive statistics (number of subjects, arithmetic mean, geometric mean, SD, geometric and arithmetic CV, median, min, and max) will be used to summarize the calculated PK parameters by treatment, day and analyte. For  $t_{max}$ , only median, min and max will be presented.

The points to be included in the  $\lambda z$  range will be determined by the pharmacokineticist after inspection of the semi-log concentration-time profiles. At least 3 points will be required to be used and the range should ideally be spread over a time interval representing at least 2 half-lives. The  $C_{max}$  data point will not be included.

Parameters based on  $R^2$  below 0.70 or %AUCextra above 20% will be flagged and excluded from descriptive statistics.

The ratio of geometric means from the microdose IV kinetics with that from the oral dose will be estimated using an analysis of variance (ANOVA) of the natural logarithm transformed clearance (CL and CL/F). A mixed model will be used, separately for the 2 cohorts with the 2 doses of 10mg and 50mg, and will include fixed effects for route (oral or iv) and for day (1 and 14) and a random effect for subject. From this model the least-squares means (LSMeans) for clearance (CL) of [C]-balovaptan iv and for CL/F of oral balovaptan will be presented. The ratios of the LSMeans for the comparison of CL to CL/F (IV/Oral) will be obtained by exponentiating the difference of the LSMeans on the log scale. A 90% confidence interval for the ratios of the treatment means will be calculated.

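### The 90% CI for the CL versus CL/F ratio uses a pooled residual that is the wrong error term for F once Day 14 values enter the model; the direction and size of the error cannot be known from the documents

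*SAP*

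**What the plan says.** SAP 16.2.2 analyses log-transformed CL (tracer, IV) and CL/F (oral), "separately for the 2 cohorts with the 2 doses of 10mg and 50mg". Each model "will include fixed effects for route (oral or iv) and for day (1 and 14) and a random effect for subject". No subject-by-route or subject-by-day random effect, covariance structure, route-by-day term or df method is given. The IV/oral ratio is the exponentiated difference of the route LSMeans, and "A 90% confidence interval for the ratios of the treatment means will be calculated". This goes into Table 14.2.7 and is the only confidence interval planned for F.

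The sample size was set on precision, "with the target of at least 6 subjects available for the primary PK analysis". At 35% within-subject variability, the 90% limits "would be obtained by dividing/multiplying the ratio estimate by a factor of 1.50" (SAP 6.1; Protocol 6.1, whose Table 4 adds 1.42 at 30% and 1.59 at 40%). The primary parameter is F after the single 10 mg dose (Protocol 6.6).

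**The concern.** The infusion starts 1.25 hours after the oral dose on both full-profile days (Protocol 4.3.2.2). Within one subject and day, ln CL minus ln(CL/F) is ln F, and whatever clearance was on that day drops out. What limits the precision of mean F is how much ln F differs between subjects.

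With two routes and two days there are four values per subject. A subject intercept alone assumes that, beyond it, the four values are independent. Two things then go wrong:

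- A subject whose F is high on Day 1 and again on Day 14 is counted as two independent pieces of evidence.
- A subject whose clearance changes between the days adds that change to the error, although it has no bearing on F.

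The first makes the interval too narrow and the second makes it too wide. Since the study was sized only for the precision of F, the stated precision may not mean what it says.

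**Working it through.** **The plan's own figure.** Inputs from Protocol 6.1: n=6, s=0.30, 0.35 and 0.40 used directly as log-scale SDs, two-sided 90%. Paired, single occasion, 5 df:

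factor = exp(t(0.95, 5) × s × √(2/6)), with t = 2.015

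This gives 1.42, 1.50 and 1.59, matching Table 4. The planning is therefore a single-occasion paired calculation on n-1 df.

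**Error term of the SAP model.** Let S_SR be the subject-by-route variance (persistent differences in F), S_SD the subject-by-day variance (clearance change shared by both routes) and S_E the remainder. With complete data, the residual has 4n - 3 - (n-1) = 3n-2 df, which is 16 at n=6. It pools:

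- subject-by-route: 5 df, expectation S_E + 2·S_SR
- subject-by-day: 5 df, expectation S_E + 2·S_SD
- the rest, including the omitted route-by-day term (no true change in F assumed): 6 df, expectation S_E

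Pooled expectation: S_E + (10/16)(S_SR + S_SD) = S_E + 0.625(S_SR + S_SD).

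The variance of the day-averaged log ratio is (S_E + 2·S_SR)/n, so the error term needed is S_E + 2·S_SR, on 5 df. The two expectations agree when 2·S_SR = 0.625(S_SR + S_SD), that is S_SR = (0.625/1.375)·S_SD ≈ 0.45·S_SD. Above that the SE is too small on average; below it, too large.

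**Worked cases, n=6.** Per-occasion variance of ln F is set to 2 × 0.35² = 0.245. The share persistent within a subject (ρ) and the occasion SD of clearance are assumptions.

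- ρ=0.9, occasion SD 0: S_SR = 0.9 × 0.245/2 = 0.110 and S_E = 0.1 × 0.245/2 = 0.012. Needed 0.233; pooled 0.081. SE ratio √(0.081/0.233) = 0.59.
- ρ=0, occasion SD 0.35: S_E = 0.1225 and S_SD = 0.1225. Needed 0.1225; pooled 0.199. SE ratio √1.625 = 1.27.

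**Simulated coverage of the nominal 90% interval, n=6** (60,000 trials per setting):

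| ρ | Occasion SD of CL | SAP model | Paired, day-averaged (5 df) |
|---|---|---|---|
| 0 | 0 | 90.0% | 90% |
| 0 | 0.35 | 95.6% | 90% |
| 0.5 | 0 | 78.0% | 90% |
| 0.5 | 0.2 | 82.4% | 90% |
| 0.5 | 0.35 | 88.9% | 90% |
| 0.9 | 0 | 65.7% | 90% |
| 0.9 | 0.35 | 81.9% | 90% |

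At n=8 the range over the same kind of settings is 66.7% to 95.8%, so full enrolment does not help. The paired Day 1 interval also covers 90% throughout.

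Settings given directly as SDs, n=6:

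- Persistent SD(ln F) 0.30, occasion SD of CL 0.30, occasion SD of F 0.10, residual SD 0.10: 88%.
- SD(ln F) 0.10, occasion SD of CL 0.30, residual SD 0.05: 99%, with a factor of about 1.18 where 1.09 is correct.

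**Adding only a fixed route-by-day term.** Day 1 coverage at n=6 is then 81% to 96%, so the error term is still wrong.

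**The case against.** **1.28 against 1.50.** With s=0.35 and independent residuals, the SAP model gives exp(1.746 × 0.35 × √(2/12)) = 1.28. A reader might take the gap from 1.50 as the size of the fault. It is not. The paired interval for the same two-day average is exp(2.015 × 0.35 × √(2/12)) = 1.33, so most of the gap comes from averaging two days. The step from 1.33 to 1.28 is extra df that are legitimate under that independence assumption, where coverage is 90.0%.

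**Unequal variances.** Protocol 6.1 refers to "IV kinetics, which is expected to be less variable than oral kinetics", and a reader might infer that equal-variance pooling is what breaks the interval. If the routes differ only in residual variance (a and b), the route, day and route-by-day contrasts all have variance (a+b)/2 and the pooled residual stays unbiased. Residual SDs of 0.20 and 0.45 give about 89% coverage at n=6, as do 0.10 and 0.48. This is not a material problem.

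**Low coverage as a prediction.** The figures near 66% need large persistent F differences and little clearance drift. The documents do not establish that. They describe the PK as time-dependent (Protocol 3.3.2), so subject-by-day variation may not be small, and balanced components give 88-89%.

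**Table 1.** SAP Table 1 lists AUC0-inf for Period 1 only, and CL, CL/F and F all rest on it. If only Day 1 enters, route plus random subject is exactly the paired 5-df analysis and the fault disappears. However, the model names Day 14, and SAP 5.2.1 lists CL on both days. The objection shows a contradiction to resolve; it does not dispose of the point.

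**Limited consequence.** SAP 9.4.3 states: "No formal hypothesis testing will be done". F is calculated per subject and summarised by treatment and day with geometric mean and CV, so a paired interval could be recovered from planned output. This stands and lowers the severity.

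**Conclusion.** The concern holds, conditionally. If Day 14 values enter as SAP 16.2.2 says, the interval's error term is not the one that F requires, and the model does not perform the paired calculation behind the planned 1.50. Coverage is nominal only if persistent F differences and subject-specific clearance drift are both absent or happen to offset.

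Neither direction nor size can be stated from the documents, because they do not split the within-subject variance. The supportable statement is the whole range at n=6: about 66% to 99% for a nominal 90% interval, with 88-90% when the components balance or are absent. A claim that the interval will be too narrow goes beyond the documents. The df and coverage figures assume complete data and residual-type df, as the SAP names no df method.

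Should-fix: the reported precision of the primary parameter is affected, but no test or decision threshold depends on it.

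**What to change.** In SAP 16.2.2, compute ln F = ln CL - ln(CL/F) for each subject and day. Report geometric mean F with a 90% one-sample t interval (n-1 df) by cohort and day, naming Cohort 1 Day 1 as primary. This matches the calculation behind 1.50 and also ends the averaging of Day 1 with Day 14.

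If a single mixed model is kept, it needs a fixed route-by-day term plus random subject-by-route and subject-by-day effects, with Kenward-Roger df. An unstructured 4×4 within-subject covariance is not a practical alternative: it has 10 parameters for 6 to 8 subjects.

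Reconcile Table 1 with the use of Day 14 CL and CL/F, stating which AUC they rest on.

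The cost is a few lines of SAP text and a simpler program. The downside is that the reported interval may be wider than the current model would show.

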## 17.0 Safety Analyses

### 17.1 Safety Variables

Physical examination and body weight (including BMI) will be listed according to scheme times.

The following safety variables will be summarized:

- AEs
- Vital Signs
  - Supine Blood Pressure
    - Systolic Blood Pressure (SBP)
    - Diastolic Blood Pressure (DBP)
  - Pulse rate
  - Body temperature (tympanic)
  - Respiratory rate
- Electrocardiograms (ECG)
  - Heart Rate
  - PR Interval
  - QRS-Duration
  - QT Interval
  - QTc (Fridericia) Interval
  - T-Wave
  - U-Wave
- Clinical Laboratory Evaluations
  - Serum Chemistry
  - Hematology
  - Urinalysis
  - Coagulation
- Columbia-Suicide Severity Rating Scale (C-SSRS)
  - Suicidal ideation
  - Suicidal behavior

### 17.1.1 Adverse Events

All AEs will be coded to the current version of Medical Dictionary for Regulatory Activities (MedDRA, the latest version) by F. Hoffmann-La Roche, Ltd.

All AE summaries will include only treatment emergent adverse events (TEAEs). Treatment-emergent adverse events are those which occur after the first dose of study drug. AEs starting prior to medication dosing in the first period will be regarded as pre-dose AEs (i.e. non-TEAEs).

TEAEs occurring following dosing in a specific analysis period but before dosing in the next analysis period will be attributed to that specific analysis period, thus to the last received treatment. If the time is missing for an AE on a dosing day then the AE will be attributed to the treatment given on that day.

All AEs (including non-TEAEs) recorded on the eCRF will be listed (including analysis period and treatment information). Pre-dose AEs will be presented in a separate listing. In addition, a separate listing of AEs leading to withdrawal from study will be provided.

TEAEs will be tabulated by system organ class and preferred term: one table with all TEAEs (number and percentage of subjects) overall and by treatment; one table with related TEAEs (number and percentage of subjects) overall and by treatment; one table with all TEAEs (number and percentage of subjects) by treatment and relationship to study drug; one table with TEAEs (number and percentage of subjects) by treatment and severity.

Subjects are counted once, per preferred term per treatment, for the most severe of multiple occurrences (in case of severity) or most drug-related event (in case of relationship) of a specific MedDRA term. AEs whose causal relationship was characterized as 'Yes'/'No' will be regarded as being related/not related to the study medication.

The following missing data will be imputed as defined (for calculations only / will not be presented):

- Missing AE start and / or end times for the calculation of onset and duration will be assumed to be at 00:01 for a start time and 23:59 for end times

- Missing AE severity or relationship will be assumed to be severe or related, respectively
- Missing AE start times for the determination of treatment emergence will be assumed to occur after treatment unless partial date documents the AE as happening prior to treatment
- Missing AE start times for the determination of treatment assignment will be assumed to occur after treatment on the recorded date one minute after dosing
- Missing AE start date will be attributed to the treatment from analysis period 1 unless the AE end date occurs before first IMP administration

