3. STUDY DESIGN

3.1 DESCRIPTION OF THE STUDY

This study will be a non-randomized, open-label, parallel group, two-treatment study in healthy volunteers to investigate the absolute oral bioavailability of balovaptan. The study will be conducted at 1 site in the Netherlands.

Screening

Screening will be conducted up to 28 days prior to admission to the clinical research unit (CRU).

In-Clinic Confinement

Subjects will be in the CRU for 2 study periods. In both periods, subjects will be admitted on Day -1 (the day before dosing begins). Day 1 will be the first day of dosing. In Period 1, subjects will be discharged on Day 10 after all assessments have been completed. There will be a wash-out period of 14 days between Day 1 of Period 1 and Day 1 of Period 2.

Subjects will be readmitted to the CRU for a second in-house period on Day 14 of Period 1 (Day -1 of Period 2) to begin Period 2. Day 1 will be the first day of dosing. In Period 2, subjects will be discharged in the morning of Day 19.

During the in-house stays and screening and follow-up visits, subjects will undergo assessments as outlined in the schedule of activities ([Appendix 1](#)), including assessments of AEs and concomitant medications, vital signs, electrocardiograms (ECGs), clinical laboratory evaluations, and blood sampling for PK evaluations. ■

Dosing

Two cohorts of 8 subjects each will be included in the study. The 2 cohorts will receive the following treatment regimens:

Cohort 1

Period 1:

- Day 1: a single oral dose of 10 mg balovaptan after at least 10 hours of fasting, followed 1.25 hours later by a 15-minute intravenous (IV) infusion of [¹³C]-labeled balovaptan 0.1 mg.

Period 2:

- Day 1 to Day 14: oral doses of 10 mg balovaptan QD; on Day 7 and Day 14 study drug administration will take place after at least 10 hours of fasting.
- Day 14: the final oral dosing will be followed 1.25 hours later by a 15-minute IV infusion of [¹³C]-labeled balovaptan 0.1 mg.

Cohort 2

Period 1:

- Day 1: a single oral dose of 50 mg balovaptan after at least 10 hours of fasting, followed 1.25 hours later by a 15-minute IV infusion of [¹³C]-labeled balovaptan 0.1 mg.

Period 2:

[figure not shown]
- Day 1 to Day 14: oral doses of 50 mg balovaptan QD; on Day 7 and Day 14 study drug administration will take place after at least 10 hours of fasting.
- Day 14: the final oral dosing will be followed 1.25 hours later by a 15-minute IV infusion of [¹³C]-labeled balovaptan 0.1 mg.

Follow-up

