Subjects will return for a follow-up visit between 14 and 21 days after the last dose. Follow-up visit will include a physical examination (excluding height), routine safety laboratory tests, 12-lead ECG (single) and vital signs (systolic and diastolic blood pressure and pulse rate).

Figure 1 presents an overview of the study design. A schedule of activities is provided in Appendix 1.

Figure 1 Study Schema

IV = intravenous; QD = once daily

^a Day 14 of Period 1 is Day -1 of Period 2

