4.3.2.1 Balovaptan (Oral Administration)

An oral dose of balovaptan 10 mg (Cohort 1) or 50 mg (Cohort 2) will be administered in the morning of Day 1 of Period 1 and each morning of Days 1 to 14 of Period 2. On Days 1 of Period 1 and Days 7 and 14 of Period 2, study drug administration will be after an overnight fast of at least 10 hours, followed by another 4 hours of fasting until lunch. On the other dosing days, study drug administration will take place at least 30 minutes before breakfast. Water will be allowed ad libitum until 1 hour prior to dosing and from 1 hour post dosing, and a maximum of 3 liters a day.

Study drug will be swallowed whole with 240 mL of still water.

4.3.2.2 [¹³C]-Labeled Balovaptan

On Day 1 of Period 1 and on Day 14 of Period 2, a single microdose of [¹³C]-labeled balovaptan 0.1 mg will be administered by a 15-minute constant IV infusion. The IV infusion will start 1.25 hours after administration of the oral dose of unlabeled balovaptan on Day 1 of Period 1 and Day 14 of Period 2.

Details on study drug preparation by the PRA Health Sciences (PRA) pharmacy will be described in the Manufacturing Batch Record, which will be prepared by the PRA pharmacy.

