5.3.1 Adverse Event Reporting Period

Investigators will seek information on AEs at each subject contact. All AEs, whether reported by the subject or noted by study personnel, will be recorded in the subject's medical record and on the Adverse Event eCRF (and Form, if appropriate).

After informed consent has been obtained but prior to initiation of study drug, only SAEs caused by a protocol-mandated intervention (e.g., invasive procedures such as biopsies, discontinuation of medications) should be reported (see Section 5.4.2 for instructions for reporting SAEs).

After initiation of study drug, all AEs will be reported until up to 21 days after the last dose of study drug.

Instructions for reporting AEs that occur after the AE reporting period are provided in Section 5.6.

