### 9.2.3 Common Variable Derivations

Variable	Data Type	Definition/Calculation	Note
Change from Baseline	All	Post-dose Observation minus Baseline Observation	
Analysis Period	All	Time period starting 1 day before dosing of each of the treatments and ends 1 day before dosing in next analysis period or at the start of the follow-up period for the last treatment.	
Analysis Study Day (Prior to first Dose)	All	Date of Measurement minus Dose Date	
Analysis Study Day (Post first Dose)	All	Date of Measurement minus Dose Date +1	

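### AE percentages for single-dose and QD treatments cover windows of unequal length (14 days against 18 to 34), and the SAP conflicts with itself on where the QD window ends

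*SAP*

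**What the plan says.** SAP 17.1.1 sets the attribution rule: "TEAEs occurring following dosing in a specific analysis period but before dosing in the next analysis period will be attributed" to that period, "thus to the last received treatment". It gives no upper limit after the last dose of Period 2. The four planned tables (14.3.1.1 to 14.3.1.4) report number and percentage of subjects by treatment. Under SAP 9.1.3 the denominator is the number of subjects exposed within a treatment.

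The calendar comes from the protocol:

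- Section 3.1: "There will be a wash-out period of 14 days between Day 1 of Period 1 and Day 1 of Period 2".
- Section 4.3.2.1: in Period 2 the oral dose is given "each morning of Days 1 to 14 of Period 2".
- Section 3.1: "In Period 2, subjects will be discharged in the morning of Day 19".
- Section 3.1: "Subjects will return for a follow-up visit between 14 and 21 days after the last dose".
- Section 5.3.1: "After initiation of study drug, all AEs will be reported until up to 21 days after the last dose of study drug".

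SAP 9.2.3 defines the Analysis Period differently from the rule in 17.1.1. The period begins one day before dosing and "ends 1 day before dosing in next analysis period or at the start of the follow-up period for the last treatment". Neither document says when the follow-up period starts.

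**The concern.** The AE tables place the single-dose and QD treatments of the same subjects in adjacent columns. If one column covers more days, more background events fall into it whatever the drug does. There is no placebo arm to show the background rate, and the tables give no time at risk that would let a reader allow for it. Safety and tolerability of 10 mg and 50 mg QD is a secondary objective. A higher percentage under B than A, or under D than C, could be read as an effect of repeated dosing when part of it reflects a longer window.

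The SAP also allows different tables from the same data. SAP 17.1.1 sends a completer's follow-up AEs to B or D. SAP 9.2.3 can be read as placing them in no analysis period. Two programmers could both claim to have followed the plan.

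**Working it through.** **Reproducing the plan's figure.** Figure 1 notes that Day 14 of Period 1 is Day -1 of Period 2. Day 1 of Period 2 is therefore Day 15 of Period 1, and 15 - 1 = 14 days. This agrees with the wash-out interval in protocol 3.1, and it is the A/C window under SAP 17.1.1.

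**The B/D window.** The documents give no figure, so it has to be built from the calendar. The last dose (Day 14) is 13 days after the first.

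| Where the Period 2 window ends | Days from first Period 2 dose | Ratio to 14 days |
|---|---|---|
| Day 19 discharge (one reading of SAP 9.2.3) | 19 - 1 = 18 | 1.29 |
| Follow-up visit at its earliest | 13 + 14 = 27 | 1.93 |
| End of AE reporting, or latest follow-up visit | 13 + 21 = 34 | 2.43 |

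If 9.2.3 means the follow-up visit itself, the window is 27 to 34 days. The choice therefore moves the B/D window between 18 and 34 days. There is also a one-day mismatch at the other boundary: 9.2.3 moves from Period 1 to Period 2 one day before dosing, whereas 17.1.1 keeps events before that dose in Period 1.

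**Size in expectation.** The documents give no background AE rate, so the rates below are assumptions. With a constant rate r per subject-day and no drug effect, the probability of at least one AE in T days is 1 - exp(-r x T). At r = 0.02 the four windows give:

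- T = 14: 1 - exp(-0.28) = 24.4%
- T = 18: 1 - exp(-0.36) = 30.2%
- T = 27: 1 - exp(-0.54) = 41.7%
- T = 34: 1 - exp(-0.68) = 49.3%

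The same formula over a range of rates gives:

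| Assumed rate per subject-day | A/C, 14 days | B/D, 18 days | B/D, 27 days | B/D, 34 days |
|---|---|---|---|---|
| 0.01 | 13.1% | 16.5% | 23.7% | 28.8% |
| 0.02 | 24.4% | 30.2% | 41.7% | 49.3% |
| 0.03 | 34.3% | 41.7% | 55.5% | 63.9% |

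In subjects out of 8 at 0.02 per day, this is 8 x 0.244 = 2.0 for A/C, against 2.4, 3.3 or 3.9 for B/D.

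**What 8 subjects would show.** Take an assumed 14-day percentage p and no drug effect, so that the 34-day percentage is 1 - (1 - p)^(34/14). Two binomial counts with n = 8, treated as independent, then give:

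| Assumed 14-day percentage | Expected 34-day percentage | P(B/D higher) | P(equal) | P(B/D lower) |
|---|---|---|---|---|
| 10% | 22.6% | 0.64 | 0.22 | 0.14 |
| 20% | 41.8% | 0.76 | 0.14 | 0.11 |
| 30% | 57.9% | 0.82 | 0.10 | 0.08 |
| 50% | 81.4% | 0.87 | 0.08 | 0.05 |

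An observed rise is likely on the longest window but not certain.

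**The case against.** The strongest reply has four parts.

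1. **No planned contrast is harmed.** The safety objective names the QD regimens, SAP 9.4.3 plans no hypothesis tests, and no section plans to compare AEs between single and repeated dosing. The dose comparisons, A with C and B with D, have equal windows. One dose and 14 daily doses differ by design in any case. This stands and limits the weight of the point. It does not make the adjacent columns comparable, and descriptive tables are read across columns.
2. **The information is already there.** All AEs are listed with analysis period and treatment, related events have their own table, and with 16 subjects a reader can trace follow-up events by hand. This is partly true. It does not settle which events the tables should contain.
3. **Attribution to the last treatment is sensible.** Protocol 1.2.1.1 gives a half-life of about 46 hours after the Day 14 dose. A window closing 14 days after the first Period 2 dose ends about 24 hours after the last dose, when 2^(-24/46), or about 70%, of the concentration remains. Five half-lives run to 5 x 46 = 230 hours, about 9.6 days. Moving later events out of the QD column would separate them from the exposure that might have caused them. This stands, and is why the full B/D column should be kept.
4. **A constant rate is a simplification.** AEs are probably picked up differently in-house and in the outpatient interval before follow-up. This also stands, so the percentages above are illustrations.

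A reader might go further and infer that AE percentages must rise from A/C to B/D by construction, or that every follow-up AE goes to the QD treatment. The documents support neither. The rise is an expectation under an assumed background rate. SAP 17.1.1 also attributes AEs with a missing start date to Period 1, unless they ended before first dosing, which works the other way. SAP 9.2.3 may exclude follow-up events from Period 2, and a subject who stops after Period 1 would have follow-up events assigned to A or C.

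**Conclusion.** The point holds. Under SAP 17.1.1 the A/C columns cover 14 days and the B/D columns up to 34, the tables carry no time at risk, and the two sets of percentages are not comparable. SAP 9.2.3 and 17.1.1 conflict on whether follow-up AEs belong to B/D, and this needs correcting on any reading.

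The ratio of window lengths is 1.29 if Period 2 closes at discharge and 1.93 to 2.43 if it runs to the follow-up visit or the end of AE reporting. At an assumed 0.02 AEs per subject-day with no drug effect, this means 24% against 30% to 49% in expectation. The window lengths follow from the documents. The percentages rest on the assumed constant rate. The effect is confined to reading single dose against QD in descriptive tables; the PK endpoints and the comparisons between dose levels are untouched.

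**What to change.** - Reconcile SAP 9.2.3 with 17.1.1 by stating one end for the Period 2 AE window, defining the start of follow-up, and using the same boundary between Periods 1 and 2 in both sections.
- Keep the full B and D columns with all treatment-emergent AEs attributed to the last treatment, so that events during residual exposure stay with QD dosing.
- In Tables 14.3.1.1 to 14.3.1.4, add two sub-columns under B and D: onset within 14 days of the first Period 2 dose, and later onset.
- Show subject-days at risk in every column header. With 8 completers this would be 8 x 14 = 112 for A or C, and up to 8 x 34 = 272 for B or D.
- Base any statement on single dose against QD on the equal-length window or on AEs per subject-day, and note that dosing and in-house time still differ.

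The cost is SAP wording and extra columns in four tables. No new data are needed.
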